6.2 Demographics and Baseline Characteristics

All parameters (except birth date) mentioned in chapter 4.1 will be summarised descriptively. Appropriate exploratory p-values of t-test (unequal variances) or chisquare test to test on differences between treatment groups will be shown.

6.3 Prior and Concomitant Diseases

Concomitant diseases will be coded by MedDRA (Medical Dictionary for Regulatory Activities) terminology and presented by number and percentages within preferred term and system organ class (current version).

6.4 Prior and Concomitant Medication/Therapies

Concomitant medication/therapies and pain medication will be coded using the current WHO drug dictionary version and will be presented within ATC-2 and ATC-4 level.

Patients with at least one concomitant medication/therapy will be displayed by number and percentages.

6.5 Extent of Exposure / Compliance

The number of capsules used since last visit will be summed up for each patient to a total of capsules used. The following compliance calculation will be tabulated:

$100 * ((\text{total number of used capsules}) / \text{number of days between randomisation and study end})$

The compliance will be analysed by descriptive methods.

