## Synopsis

Title	Hydroxychloroquine in pediatric ILD. START randomized controlled in parallel-group, then switch placebo to active drug, and STOP randomized controlled in parallel-group to evaluate the efficacy and safety of hydroxychloroquine (HCQ)
Short title	HCQ in pediatric ILD
EudraCT	2013-003714-40
IZKS trial code	2013-006
Indication	Diagnosed children's interstitial lung disease (chILD) in children and adults
Phase	2a
Treatments	
Test product: Hydroxychloroquine Sulfate (HCQ), one daily dose in the evening.
 
Reference therapy: Placebo
 
The treatments are organized in START and STOP blocks, which can be initiated in sequence, as needed by the subjects.

	START HCQ block
Block specific inclusion criterion (others see 3.6.1)	All subjects not currently on HCQ (last dose $\geq$ 3 months ago) and intention to widen treatment.
Primary objective	To evaluate the efficacy of HCQ after 28 days of treatment in chILD compared to placebo
Secondary objectives	
To evaluate the efficacy of HCQ after 56 days of treatment in chILD compared to 28 days
 
To evaluate the safety of HCQ after 28 and 56 days of treatment in chILD
 
To evaluate blood levels of HCQ after 28 and 56 days of treatment in chILD

Trial design	
Double blinded treatment
 
This is an exploratory Phase 2a, randomized, double-blind, placebo-controlled, parallel-group study and switched placebo to active drug, multicentre, multinational study in subjects with chILD genetically, histologically or clinically diagnosed.
 
This study includes:
 
 
• Screening Period (Day -28 through Day -3)
 
• Treatment Period (Day 1 through Day 56)
 

	STOP HCQ block
Block specific inclusion criterion (others see 3.6.1)	All subjects on chronic (> 3 months) treatment with HCQ (usually 6-10 mg/kg/d or individually tolerated dose) and intention to reduce treatment.
Primary objective	To evaluate the efficacy of HCQ after 84 days of treatment in chILD compared to placebo
Secondary objectives	To evaluate the efficacy of chronic (> 3 months) HCQ treatment in chILD compared to placebo To evaluate the safety of HCQ after > 3 months of treatment in chILD To evaluate blood levels of HCQ before and after treatment in chILD

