Trial design	
Stop HCQ block
 
Open label treatment      Double blind treatment      Open observation
 
> 3 month      3 months      3 months
 
Stable baseline for -30 to -10 days
 
HCQ individual dose
 
no major changes in respiratory status or medication
 
Randomized withdrawal
 
placebo
 
No medication

This is an exploratory Phase 2a, randomized, double-blind, placebo-controlled, parallel-group, multinational withdrawal study in subjects with chILD and treated with hydroxychloroquine.

This study includes:

- History of Open Treatment Period (total of at least 3 months of continuing HCQ treatment until randomization)
- Screening Period (Day -30 through Day -10)
- Treatment Period (Day 1 through Day 84)
- Open observation period (Day 85 through Day 168)

Trial population	In addition to the block specific inclusion criterion the inclusion criteria are: See 3.6.1 in the protocol Allowed previous medication: see 4.1.10
	exclusion criteria: See 3.6.2
Trial duration	Until 2024/2025
Number of subjects	It is planned to enrol at least 80 subjects
Number of sites	Up to 100 trial sites are planned to participate
Primary outcome	START HCQ block Relative change trial day 1 (i.e. Visit 2) through day 28 (i.e. Visit 3) and relative change day 28 to day 56 (i.e. Visit 4) active compared to change placebo STOP HCQ block Relative change day 1 (i.e. Visit 2) through day 84 (i.e. Visit 5): change active compound compared to change placebo Oxygenation (see Table 3.3-1)
Secondary outcome	See 3.4

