## STOP HCQ block

Table 1-2

Visit	Visit 1 + Screening	Visit 2	Email- /Phone- Visit	Visit 3	Email-/ Phone- Visit	Visit 4	Email-/ Phone- Visit	Visit 5	Email-/ Phone- Visit	Visit 6	Email- /Phone- Visit	Visit 7	Email- /Phone- Visit	Visit 8
Action	„Begin of baseline“	“End of baseline“ + Day 1 of withdrawal treatment	2 weeks of withdrawal, at home	4 weeks of withdrawal treatment	6 weeks of withdrawal, at home	8 weeks of withdrawal treatment	10 weeks of withdrawal, at home	“End of trial“ after 12 weeks of withdrawal treatment	2 weeks of open observation at home	Follow up after 4 weeks of open observation	6 weeks of withdrawal, at home	Follow up after 8 weeks of open observation	10 weeks of withdrawal, at home	Follow up after 12 weeks of open observation
Trial day	-30 to -10	1	14 (-7, +7)	28 (-7, +7)	42 (-7, +7)	56 (-7, +7)	70 (-7, +7)	84 (-7, +7)	98 (-7, +7)	112 (-7, +7)	126 (-7, +7)	140 (-7, +7)	154 (-7, +7)	168 (-7, +7)
Demographics (e.g. sex, age)	X													
Patient information, informed consent	X													
Previous (last 12 months) and concomitant diseases	X	X	X	X	X	X	X	X	X	X	X	X	X	X
Previous (last 3 months) and concomitant treatments	X	X	X	X	X	X	X	X	X	X	X	X	X	X
Inclusion/exclusion criteria	X	X 												
Pregnancy test k	X*			X		X		X						
Randomization a	X													
Trial medication supply to patient		X		X		X								
History (cardiotoxicity, hypoglycaemia)	X	X		X		X		X		X		X		X
Physical examination	X	X		X		X		X		X		X		X
Vital signs (BP, pulse, temp) b	X	X		X		X		X		X		X		X
ECG j	X*							X						X
Ophthalmologic review l	X*													X 
Lab c (GOT/GPT/Crea/Potassium/CK/gGT/LDH/BB/DIF F / HCQ drug level, blood glucose)	X*			X		X		X		X (only HCQ drug level)		X (only HCQ drug level)		X (only HCQ drug level)
pO 2 , pCO 2 (capillary)	X	X 		X 		X 		X 		X 		X 		X 
O 2 -sat e , in room air	X	X	X	X	X	X	X	X	X	X	X	X	X	X
Respiratory rate, in room air	X	X	X	X	X	X	X	X	X	X	X	X	X	X

CONFIDENTIAL

Visit	Visit 1 + Screening	Visit 2	Email- /Phone- Visit	Visit 3	Email-/ Phone- Visit	Visit 4	Email-/ Phone- Visit	Visit 5	Email-/ Phone- Visit	Visit 6	Email- /Phone- Visit	Visit 7	Email- /Phone- Visit	Visit 8
Retractions	X	X	X	X	X	X	X	X	X	X	X	X	X	X
Coughing	X	X	X	X	X	X	X	X	X	X	X	X	X	X
Oxygen demand c	X	X	X	X	X	X	X	X	X	X	X	X	X	X

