a Randomization must occur for logistic reasons as soon as possible after concluding all screening investigations and including the patient into the study. This secures delivery of the study medication in time to any study center.

b Weight (kg) and height (cm) will be measured with shoes and clothes off. Vital signs will be collected after the patient has been at rest for 5 minutes.

c Blood sample should include: Blood count with differential, GOT, GPT, gGT, Creatinine, LDH, Potassium, Creatine kinase, blood glucose. HCQ drug level (2 ml EDTA blood and 2 ml of Serum blood). Labor Manual will be provided.

d Spirometry / Bodyplethysmography will be performed pre-bronchodilator in children age  $\geq$  5 years. (If a child  $\leq$  5 years is already able to perform the listed investigations (spirometry or bodyplethysmography), these should also be performed and documented at the discretion of the investigator) The following lung function parameters will be assessed: FEV1 % predicted (recorded in L), FEV 1 (L), FVC % predicted (recorded in L), FVC (L); MEF 75 (L/s); MEF 50 (L/s); MEF 25 (L/s); TLC (L); ITGV (L); RV (L); R eff (kPa\*s/L); R eff predicted (%). SOP will be provided.

e Measurement of O2-Saturation, respiratory rate and O2 flow (if necessary) in awake patient at rest:

If not on O2: after 5 min at rest, room air, then measure twice over 1 min. each; the measurements have to be at least 1 min. apart; report the stable average value

If on O2:

- BEFORE withdrawal (after 5 min at rest with steady state O2 supplement, measure over 1 minute)
- Then withdraw O2 to obtain steady state O2-Sat. in room air (at least 30 seconds without change). Then measure twice over 1 min. each; the measurements have to be at least 1 min. apart; report the stable average value. If the O2-Sat falls below SpO2<80% place back in oxygen and note as exact value.

Document the time of measurement and state of the patient, usually "awake, at rest". Note: In babies avoid crying, eating, sleeping during measurement. Note: try to schedule patients at similar time of the day.

f Borg-Scale: assessment of dyspnea (0 – 10: 0 = no dyspnea at all, 5 = severe dyspnea, 10 = extremely severe dyspnea)

g Standard exercise testing (6-minute-walk test): SOP will be provided

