#### 4.1.6 Drug distribution to subjects

For all patients capsules with individual, body weight adjusted drug or placebo will be manufactured and shipped by the pharmacy within a week to the site for distribution to the patients or their caregivers. No adjustments of dose are necessary throughout the trial, as all patients will receive their body adjusted dose from the beginning.

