Oxygenation index (OI)	X	X	X	X	X	X	X	X	X
Duration (h) of mechanical ventilation	X	X	X	X	X	X	X	X	X
NO (%) ^g , ECCL (VVVA/ECCL)Flow/time since insertion	X	X	X	X	X	X	X	X	X

X* Tests must be done before first drug dosing

X** Test can be done facultative, but should be done, if initial pCO₂ has been elevated

X*** Chest x-ray is recommended if clinically indicated e.g. to answer the question if the disease is stable

a Randomization must occur after all inclusion and exclusion criteria are met directly after consent to the study is given and at least 1 week before first dose of HCQ or withdrawal treatment. This is necessary to allow for preparation and shipping of the study medication.

c Blood sample should include: Blood count with differential, GOT, GPT, gGT, Creatinine, LDH, BUN, Creatine kinase, drug level, 3 ml EDTA-blood

d Spirometry will be performed pre-bronchodilator in children age ≥ 5 years. SOP will be provided.

e Measurement of O₂-Saturation, respiratory rate and O₂ flow (if necessary) in awake patient at rest:

If not on O₂: after 5 min at rest, room air, then measure twice over 1 min. each, at least 1 min. apart

If on O₂:

- BEFORE withdrawal (after 5 min at rest with steady state O₂ supplement, then measure over 1 minute)
 - Then withdraw O₂ to obtain steady state O₂-Sat. in room air (at least 30 seconds without change). Then measure twice over 1 min. each, at least 1 min. apart. If falls below SpO₂<80% place back in oxygen and note as <80%.

f Borg-Scale: assessment of dyspnea (0 – 10: 0 = no dyspnea at all, 5 = severe dyspnea, 10 = extremely severe dyspnea)

g Standard exercise testing (6-minute-walk test): SOP will be provided

h Health economics assessment with the use of a special questionnaire which has to be filled out by the parents

i Quality of Life assessment with the use of the questionnaire PedsQL for different age groups

j For ophthalmological review please see Chapter 5.1

k Pregnancy test only has to be performed in girls of childbearing age and only if sexual relations are known or probable. It is at the discretion and responsibility of the attending physician to decide, whether a pregnancy test is necessary or not.

2 Analysis Populations

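### SAP 6.5 counts compliance days from randomisation rather than first dose, so at one capsule a day full adherence cannot show 100%; the SAP's STOP follow-up visits also differ from protocol Table 1-2

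*SAP*

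**What the plan says.** **Compliance.** SAP 6.5 adds up the capsules used since each last visit and expresses the total as a percentage of the "number of days between randomisation and study end". Study end is not defined there, and the formula has no term for capsules per day. The result is to be described only.

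**When randomisation happens.** All four schedule tables place randomisation in the screening/Visit 1 column. Footnote a to the SAP schedules requires it "at least 1 week before first dose of HCQ or withdrawal treatment", to leave time to prepare and ship the medication. Footnote a to the protocol schedules sets no minimum: "Randomization must occur for logistic reasons as soon as possible after concluding all screening investigations". The screening window is day -28 to day -3 in START and day -30 to day -10 in STOP (protocol Synopsis). Protocol 4.1.6 says weight-adjusted capsules are "manufactured and shipped by the pharmacy within a week to the site". Protocol Tables 1-1 and 1-2 show trial medication first supplied at Visit 2, day 1.

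**STOP follow-up.** In protocol Table 1-2, Visit 6 is day 112 ("Follow up after 4 weeks of open observation"), Visit 7 is day 140 and Visit 8 is day 168. Each has a laboratory entry marked "only HCQ drug level". The SAP's STOP schedule ends at Visit 6, which it places at day 168, and SAP 4.2.2 names Visit 6 as the only follow-up sample.

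**The concern.** A compliance percentage should read 100% when every prescribed dose is taken. Here the count of days opens before the patient has any capsules, so the figure combines two things: how well the child took the drug, and how long the interval was between randomisation and Visit 2. Two children with identical intake get different values if their intervals differ. In STOP the artefact is easy to see, because patients enter on stable HCQ and are not under-dosed while they wait for trial capsules. A reader of the table could see under-dosing that did not occur.

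The visit mismatch matters for a different output. HCQ levels before and after treatment are a named STOP secondary objective (protocol 2.2, SAP 1.1). Two planned follow-up samples have no place in the SAP schedule, and one visit number stands for two dates 56 days apart.

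**Working it through.** The documents give no compliance figure to reproduce, so the SAP formula is applied directly.

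**Inputs**
- Dosing: day 1 to 84 in STOP, day 1 to 56 in START (protocol Synopsis).
- One dose a day (protocol 4.1.1.4). One capsule per dose is an assumption; the documents do not state it.
- Every capsule taken, so the true value is 100%.
- Study end: day 84 in STOP and day 56 in START, the visits that both schedules label as the end of the trial. Day 168 is tried as an alternative for STOP.
- Lag from randomisation to day 1: the edges of the screening windows, and the SAP's 7-day minimum.

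**Formula.** Compliance = 100 × capsules used / (lag + day number of study end).

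| Block, study end | Lag (days) | Calculation | Result |
|---|---|---|---|
| STOP, day 84 | 30 | 84/114 | 73.7% |
| STOP, day 84 | 10 (end of screening window) | 84/94 | 89.4% |
| STOP, day 84 | 7 (SAP minimum) | 84/91 | 92.3% |
| START, day 56 | 28 | 56/84 | 66.7% |
| START, day 56 | 7 (SAP minimum) | 56/63 | 88.9% |
| START, day 56 | 3 (protocol window edge) | 56/59 | 94.9% |
| STOP, day 168 | 30 | 84/198 | 42.4% |
| STOP, day 168 | 7 | 84/175 | 48.0% |

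Taking simple date differences instead of inclusive day counts shortens each denominator by one day and changes little: for STOP to day 84, 84/113 = 74.3% to 84/90 = 93.3%.

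**What the statistic cannot separate.** A fully adherent STOP child with a 30-day lag shows 84/114 = 73.7%. A child with a 7-day lag who took 67 of 84 capsules (67/84 = 79.8% true adherence) shows 67/91 = 73.6%.

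**With the count started at first dose:** 84/84 = 100% in STOP and 56/56 = 100% in START.

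**HCQ levels, if a day-112 sample were read as day 168.** Assume first-order decline from day 84 in the active arm and no restart of HCQ. The fraction of the day-84 level left after t days is 2^(−t/half-life). The overstatement is the ratio of the fractions at days 112 and 168, which is 2^(56/half-life). Protocol 1.3 gives a half-life of 30 to 60 days and, in the same paragraph, a slow elimination phase of 18 days.

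| Half-life | Left at day 112 | Left at day 168 | Ratio |
|---|---|---|---|
| 60 days | 72% | 38% | 1.91 |
| 30 days | 52% | 14% | 3.65 |
| 18 days | 34% | 4% | 8.6 |

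**The case against.** **The percentages depend on choices that the documents leave open.** This stands. A reader might take 74% to 92% as what the STOP table will show. The documents do not support that. The lower end needs randomisation on the first day of the window, although the protocol places it after screening is complete. The upper end uses the SAP's 7-day minimum, although STOP screening closes at day -10, which gives 89%. In START, the protocol has no one-week minimum and its day -3 edge gives 95%. Even the direction depends on one capsule per dose: at two per dose the same formula gives 168/114 = 147% or more. That would be another fault in the formula, not a defence of it.

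**Study end could mean day 168.** The Synopsis lists open observation to day 168 as part of the STOP study. But both schedules call day 84 the end of the trial, so 42% to 48% is a possible reading and not the expected one.

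**The lag is not all shipping time.** This also stands. Protocol 4.1.6 allows about a week for making and shipping capsules, so lags of three or four weeks would mainly reflect how Visits 1 and 2 were scheduled.

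**The HCQ levels may never be mislabelled.** A reader might infer that day-112 levels will be reported as day 168. The documents do not go that far. The eCRF follows the protocol (protocol 10.1), and SAP 6.7.2.2 promises per-patient listings and summaries over time. If samples are matched by day, the day-168 value stays correct and only days 112 and 140 lack a slot. Screening, day 84 and day 168 already give levels before and after treatment. The mismatch between the two schedules remains.

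**Protocol 4.1.10 also uses V6**, as the STOP limit for its steroid rule. The SAP change below leaves that reference as it is.

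**Conclusion.** The concern holds as a minor point. Given one capsule a day, the SAP 6.5 formula cannot return 100% for a fully adherent patient in either block. The shortfall for such a patient is about 8 to 26 percentage points in STOP with study end at day 84, and about 5 to 33 points in START with study end at day 56. It varies with the interval between randomisation and Visit 2.

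A reader might infer a threat to the efficacy results. The documents do not support that: compliance is only described, SAP 2.3 rules out a per-protocol analysis, both arms share the formula, and neither the day-28 nor the day-84 primary comparison uses it.

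The Visit 6 mismatch between the two current schedules is real, but its harm is conditional. Only if tables were built on the SAP visit number could a day-112 level be read as day 168. It would then be about 1.9 to 3.7 times too high with a 30 to 60 day half-life, or about 8.6 times with the 18-day slow phase. HCQ levels at Visits 3 to 5 are unaffected.

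Confidence is high that both defects exist, and lower for the exact percentages and ratios.

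**What to change.** 1. **SAP 6.5.** Replace the denominator with the days from first dose (Visit 2) to the end of trial dosing (Visit 4 in START, Visit 5 in STOP), or to treatment stop if that is earlier, multiplied by the capsules prescribed per day. This also removes the undefined study end.
2. **SAP STOP schedule and 4.2.2.** Align both with protocol Table 1-2, name the follow-up HCQ levels as days 112, 140 and 168 (Visits 6, 7 and 8) in addition to those at Visits 3 to 5, and tabulate the follow-up levels by trial day.

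The cost is one formula, one schedule table and one sentence in the SAP, with no new visit, sample or patient and no protocol change. The new denominator needs each patient's actual first-dose date, stop date and prescribed capsules per day. The HCQ table gains two rows.

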6.6 Primary Analysis

The variable assessing the primary outcome is the response rate measured by the oxygen saturation in room air.

START HCQ block

Relative change from trial day 1 (Visit 2) to day 28 (Visit 3) and day 56 (Visit 4) and from day 28 to day 56 change from active compound compared to change from placebo

STOP HCQ block

Relative change from trial day 1, i.e. Visit 2, through day 84, i.e. Visit 5: change from active compound compared to change from placebo

Both blocks separately

a) A difference between the changes in placebo and active phases is considered significant as described in the table below.

Patient's condition	Measured parameter	Definition of significant change or responder
Stable in room air or on	SpO2 in room air	Increase $\geq 5\%$

O2-supplement		
On high-flow nasal cannula	O2-flow, air-flow	Decrease $\geq 20\%$ or support not needed any more
Ventilated	Oxygenation index	Decrease $\geq 20\%$ or support not needed any more
On ECMO		Decrease $\geq 20\%$ or support not needed any more

The analysis will be done first by discarding the information on the patient's condition. Descriptive analyses will be done overall and for all patients conditions separately.

b) Patients are defined as responder as described in the table above. The numbers of responders are counted and compared by Fisher's exact test as well as logistic regression models with factors for treatment group and age group.

The following SAS code can be used:

```
PROC LOGISTIC DATA=indata;
  CLASS treatment age_gr;
  MODEL responder_YN = treatment age_group treatment*age_group;
RUN;
```

Both blocks together

Not applicable. There were too few patients in both blocks.

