As it is not clear, if HCQ works in these conditions at all, a placebo controlled design is justified. The selected duration of the placebo phase was the result of a delphi questionnaire among European pediatric pneumologists and balanced the anticipated time point, when a treatment effect could be noted in a majority of patients if present, and the time period tolerated to withhold the drug from a placebo treated subject.

So we think, that in a patient with relatively stable disease it is justifiable to start the treatment with the study drug in the placebo arm four weeks later than in the study drug arm without relevant disadvantage for the patient, as till now we don't even know, if he will benefit from the pharmacological treatment or not. Due to this fact, we believe, that all patients should receive HCQ at one point during the study to avoid that patients who might benefit from the treatment with HCQ are not treated.

Due to the heterogeneity of the diseases with a wide spectrum of clinical symptoms and severity it is not possible to determine one specific HCQ treatment duration that will fit the majority of subjects. Physicians anticipate treatment of some patients that will be treated with HCQ only for some weeks and patients that will need HCQ treatment for several years. Due to the variety of conditions and our intention to be as inclusive as possible in this exploratory trial, we decided not to determine the time period patients are treated between the start and stop treatment with HCQ. However, we took the chance to investigate stopping HCQ in a double blind, placebo controlled fashion. As with longer treatment and the intention to terminate treatment the exact time point to stop the treatment does not matter, we suggest a placebo-controlled withdrawal of active drug. In this stop block patients on active drug are randomized in a blinded manner to either continue for three more months with their active treatment or to receive placebo.

In summary the risk of major side effects in these already often used pharmacological treatments as well as the risk of giving placebo instead of the study drug seems acceptable regarding the gain of useful knowledge and the possibility to create adequate treatment strategies for chILD.

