#### **START HCQ block**

To evaluate the efficacy of HCQ after 28 days of treatment in chILD compared to placebo.

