#### 3.3 Primary outcome parameters

##### **START HCQ block**

Relative change trial day 1 (i.e. Visit 2) through day 28 (i.e. Visit 3) and relative change day 28 to day 56, (i.e. Visit 4): change active compound compared to change placebo

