#### Controlled initiation of HCQ

Relative change trial day 1 (i.e. Visit 2), through day 28 (i.e. Visit 3) and relative change day 28 (i.e. Visit 3) to day 56 (i.e. Visit 4) active compared to change placebo

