1.2 Study Design

[figure not shown]
[figure not shown]
This study is an explorative, prospective, randomized, double-blind, placebo controlled investigation of hydroxychloroquine (HCQ) in pediatric ILD. The treatments are organized in START and STOP blocks, which can be initiated in sequence, as needed by the subjects. Each patient can participate in each block, but only once in each block.

In the START block subjects are randomized to parallel-groups, then the placebo group is switched to active drug.

In the STOP block, subjects on HCQ are randomized into parallel-groups treated with placebo or HCQ to investigate the withdrawal of HCQ for assessment of its efficacy.

It is planned to assess >100 subjects for eligibility and to allocate 80 subjects. An equal distribution between START and STOP blocks is expected.

Study flow chart

Trial schedule START HCQ Block

Visit	Screening evaluations and Visit 1	Visit 2	No Visit	Visit 3	No Visit	Visit 4
Action	„Start of baseline“	“End of baseline“ + Day 1 of treatment	Every 7 days at home + web/tele feed-back	End of 1 st Tx period	Every 7 days at home + web/tele feed-back	“End of trial“
Trial day	-28 to -3	1		28 (-4, +7)		56 (-4, +7)
Demographics (e.g. sex, age, race)	X					
Patient information, informed consent	X					
Previous and concomitant diseases	X	X		X		X
Previous and concomitant treatments	X	X		X		X
Inclusion/exclusion criteria	X					
Pregnancy test ^k	X			X		X
Randomization ^l	X					
Physical examination	X	X		X		X
Vital signs (BP, pulse, temp, cardiotoxicity, hypoglycaemia)	X	X		X		X
ECG	X*			X		X
Ophthalmologic review ^m	X*					
Lab ⁿ (GOT/GPT/Crea/BUN/CK/GGT/LDH/BB/DIFF drug level /save EDTA, blood glucose)	X*			X		X
pO ₂ , pCO ₂ (capillary)	X	X***		X***		X***
Primary outcome ^e O ₂ -sat. in room air	X	X	-	X	-	X
Secondary outcomes						
Respiratory rate, in room air	X	X	X	X	X	X
Retractions	X	X	X	X	X	X
Coughing	X	X	X	X	X	X
Oxygen demand	X	X	X	X	X	X
Chest x-ray scoring for child	X*			X****		
Pulmonary hypertension (Echo)	X*					
Quality-of-life ⁱ	X*					X
Health Economics ^h	X*					X
Weight for height ^b	X*					X
Adverse events		X	X	X	X	X
Additionally in children > 5 years						
FEV1 % predicted (recorded in L) ^d	X	X		X		X
FVC % predicted (recorded in L) ^d	X	X		X		X
6 minute walking distance (meter) ^g	X	X		X		X
O ₂ -saturation before and after 6MWT	X	X		X		X
Borg scale ^j	X	X		X		X
Additionally in ventilated patients						
Oxygenation index (OI)	X	X	X	X	X	X

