4.2 Primary Variable

START HCQ block and STOP HCQ block

The primary variable is the response rate measured by the oxygen saturation in room air.

START HCQ block

Relative change from trial day 1, i.e. Visit 2, through day 28, i.e. Visit 3, change from active compound compared to change from placebo

STOP HCQ block

Relative change from trial day 1, i.e. Visit 2, through day 84, i.e. Visit 5: change from active compound compared to change from placebo

A) Non-ventilated patients in room air or on O2-supplement

Oxygen saturation in room air

Assessment:

1) If not on O2:

(after 5 min at rest room air, then measure twice over 1 minute each, at least 1 min apart)

** O2 Sat (mean value)*

* Respiratory rate (mean value)

2) If on O2: BEFORE withdrawal:

(after 5 min at rest with steady state O2 supplement, then measured over 1 minute)

* O2 Flow

* O2 Sat (mean value)

* Respiratory rate

Then withdraw O2:

Steady state O2 Sat in air obtained. Steady state minimum SpO2 should be at least 30 seconds without change. Then measured twice over 1 minute each, at least 1 min apart.

If falls to SpO2<80% place back in oxygen and note as <80%.

* O2 Sat (mean value)

* Respiratory rate (mean value)

B) If on high-flow nasal prongs:

O2-flow and air-flow

C) Ventilated patients:

Oxygenation index (OI)

OI = (FiO2 * MPAW) / PaO2

with

FiO2 = Fraction of inspired oxygen

MPAW = Mean airway pressure (= ((frequency * inspiration time)/60) * ((inspiratory pressure (PIP) – PEEP) + PEEP)))

PaO2 = Partial pressure of oxygen in arterial blood

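### START primary analysis: SAP 6.6 labels three windows as active versus placebo, but the placebo arm is on HCQ from about day 28, so only day 1 to 28 has a placebo comparator

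*SAP*

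**What the plan says.** The START primary comparison is defined in three different ways.

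- **One window.** SAP 4.2 (Primary Variable): "Relative change from trial day 1, i.e. Visit 2, through day 28, i.e. Visit 3, change from active compound compared to change from placebo". This matches the START primary objective in Protocol 2.1: "To evaluate the efficacy of HCQ after 28 days of treatment in chILD compared to placebo".
- **Two windows.** The protocol adds day 28 to 56 to day 1 to 28, in the Synopsis ("relative change day 28 to day 56 (i.e. Visit 4) active compared to change placebo"), in 3.3 ("relative change day 28 to day 56, (i.e. Visit 4): change active compound compared to change placebo") and in 8.3.1 ("relative change day 28 (i.e. Visit 3) to day 56 (i.e. Visit 4) active compared to change placebo").
- **Three windows.** SAP 6.6 (Primary Analysis) starts with day 1 to 28 and continues: "and day 56 (Visit 4) and from day 28 to day 56 change from active compound compared to change from placebo". The active-versus-placebo label covers all three windows.

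The design statements say what the placebo arm receives. SAP 1.2: "then the placebo group is switched to active drug". Protocol 1.4 gives the timing, explaining why it is justifiable to "start the treatment with the study drug in the placebo arm four weeks later than in the study drug arm". Protocol 2.2 makes day 56 a secondary objective, set against 28 days of treatment and not against placebo.

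**The concern.** After the switch both START arms take HCQ. A day 28 to 56 or day 1 to 56 difference between arms is then a comparison of two durations or two starting times of HCQ. Calling it active versus placebo is wrong in a way that affects interpretation. The day 1 to 56 estimate would understate any HCQ effect against placebo. The day 28 to 56 estimate would tend to favour the arm labelled placebo whenever HCQ works and most of its benefit comes early. Because 6.6 places all three windows under the primary analysis, while SAP 4.2 names one and the protocol two, a programmer or reader cannot tell which START result is primary. The trial is meant to inform a risk-benefit judgement on HCQ (Protocol 1.2), so an apparently negative primary estimate could be misread.

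**Working it through.** The documents give no sample size calculation, power or alpha for this comparison, so there is no stated figure to reproduce. The check is what each window compares, followed by an illustration of size.

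**Step 1. Expected change in each arm.** Let E(t) be the HCQ effect after t days on drug, and let b1 and b2 be the background change in days 1 to 28 and 28 to 56, common to both arms by randomisation. Effects are taken as additive.

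| Window | HCQ-first arm | Placebo-first arm | Difference |
|---|---|---|---|
| Day 1–28 | b1 + E28 | b1 | E28 |
| Day 28–56 | b2 + (E56 − E28) | b2 + E28 | E56 − 2·E28 |
| Day 1–56 | b1 + b2 + E56 | b1 + b2 + E28 | E56 − E28 |

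Only the first row is HCQ versus placebo.

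**Step 2. Size as a fraction of E28.** Put f = (E56 − E28)/E28. Then day 1–56 = f·E28 and day 28–56 = (f − 1)·E28. The sign reverses when f < 1, that is, when E56 < 2·E28.

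- *Effect complete by four weeks:* f = 0. Protocol 1.4 reports that improvement usually occurs within that time, which supports a small f but does not prove it.
- *Effect proportional to drug accumulation (assumption), constant daily dose:* f = 2^(−28/half-life). Protocol 1.3 gives half-lives of 18 days (slow phase) and 30 to 60 days.
- *The same, with the seven-day loading phase of Protocol 4.1.1.4 (10, then 6.5 mg/kg/d).*

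| Case | f (day 1–56 ÷ E28) | f − 1 (day 28–56 ÷ E28) |
|---|---|---|
| Complete by 4 weeks | 0 | −1.00 |
| Half-life 18 d, constant / with loading | 0.34 / 0.26 | −0.66 / −0.74 |
| Half-life 30 d, constant / with loading | 0.52 / 0.43 | −0.48 / −0.57 |
| Half-life 60 d, constant / with loading | 0.72 / 0.62 | −0.28 / −0.38 |

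**Step 3. Responder scale.** Protocol 3.2 plans 80 subjects split equally between blocks, and 3.5.1 randomises 1:1, so 80/2/2 = 20 per START arm. Assumed rates, not from the documents: 50% respond in the first 28 days on HCQ, 10% on placebo, and 10% to 50% are new responders in the second 28 days on HCQ. For day 28–56, response is counted afresh from day 28. For day 1–56, the assumed counts are 10 to 14 of 20 against 10 of 20. P-values are two-sided Fisher.

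| Window | HCQ-first v placebo-first | Difference | p |
|---|---|---|---|
| Day 1–28 | 10/20 v 2/20 | +40 points | 0.014 |
| Day 28–56, 10% new | 2/20 v 10/20 | −40 points | 0.014 |
| Day 28–56, 20% new | 4/20 v 10/20 | −30 points | 0.096 |
| Day 28–56, 30% new | 6/20 v 10/20 | −20 points | 0.33 |
| Day 28–56, 50% new | 10/20 v 10/20 | 0 | 1.00 |
| Day 1–56, low | 10/20 v 10/20 | 0 | 1.00 |
| Day 1–56, middle | 12/20 v 10/20 | +10 points | 0.75 |
| Day 1–56, high | 14/20 v 10/20 | +20 points | 0.33 |

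**The case against.** **A within-patient reading.** SAP 6.6(a) speaks of placebo and active phases, and Protocol 1.4 calls START a cross-over, so day 28–56 might be meant as a comparison of phases within the switched patients. That does not fit the rest of 6.6: Fisher's exact test and a logistic model with a treatment-group factor compare independent groups, no paired method is given, and the reading cannot explain day 1–56. It would also be unrandomised and confounded with time.

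**Baseline for response.** The Synopsis and Protocol 8.3.1 define response against baseline. If day-56 status is judged against day 1, persistent responders give about 10/20 in both arms, which is attenuation and not reversal. This stands as a limit on the −40-point figure, which needs re-baselining at day 28. Re-baselining is, however, the literal meaning of a change from day 28 to day 56.

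**Size is illustrative.** This also stands. The response rates are assumed, the algebra is only approximate for relative changes and thresholded response, and Protocol 4.1.1.2 says the mechanism in lung disease is not understood. Ignoring the loading phase is not a way of inflating the problem: including it lowers f and makes the reversal larger.

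**Origin and consequence.** The day 28–56 window comes from the protocol; only day 1–56 is new in SAP 6.6. Day 1–28 is present in every version, so no valid estimate is lost, and the trial is exploratory. These points limit the consequence but leave the label wrong and the definitions in conflict.

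**Conclusion.** The concern holds. Of the three START windows that SAP 6.6 calls active versus placebo, only day 1–28 is one. This follows from the stated design and needs no numerical assumption. The START primary comparison is contradictorily defined: one window in SAP 4.2, two in the protocol, three in SAP 6.6.

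The size is less certain than the contradiction. With f between 0 and 0.72, the day 1–56 difference is 0 to 0.72 of the 28-day effect, and the day 28–56 difference is −1.00 to −0.28 of it. There is no reversal if the second 28 days add at least as much as the first (f ≥ 1). The harm is primary estimates that can be misread, not a breach of a formal error rate. It should be fixed.

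**What to change.** 1. In SAP 6.6 and in the Protocol Synopsis, 3.3 and 8.3.1, make day 1–28 the sole START active-versus-placebo primary contrast, as SAP 4.2 and the primary objective already do.
2. Move the between-arm day 1–56 comparison to the secondary analyses and label it early start (56 days of HCQ) versus delayed start (28 days). It can serve the existing secondary objective on 56 against 28 days. That objective could also mean day 56 against day 28 within the HCQ-first arm, so the text should say which is intended.
3. In SAP 6.7.1, state that the day-56 between-group comparison is early versus delayed start.
4. Remove the placebo label from day 28–56. If the window is kept, report it in the switched arm as a within-patient, non-randomised change on first HCQ exposure in the trial. This summary is optional; the relabelling and reconciliation are what is needed.

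The cost is SAP wording plus a protocol amendment, which Protocol 8 requires for major changes to the primary outcome or its analysis, with notice to the ethics committee. No new data or visits are needed. Day 28–56 loses its status as a primary active-versus-placebo contrast.
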